9.2 SAMPLE SIZE DETERMINATION

The sample size is 24 participants in the final dataset to be used in analysis. However, to ensure that 24 participants complete the experiment, we conservatively estimate to enroll 50 participants as a ceiling for the sake of IRB approval. The motivation for the sample size of 24 participants in the analysis is explained below. The sample size is determined based on previous experiments from our group: the effect size of previous findings and the reliability of our estimates. Our estimators are precise due to sufficient number of trials per condition with each participant and that the tasks are titrated to the individual.

Primary outcome: Rhythmic TMS to lateral frontal cortex at delta-beta frequency will increase goal-directed behavior relative to arrhythmic TMS.

Previous Data: The planning and refinement of the proposed study was informed by our previous experiments that serve as preliminary data for the proposal. In our previous experiment, we delivered rhythmic TMS to lateral frontal cortex to increase performance in a cognitive control task (Riddle et al. 2020b). In our previous study, there was a significant interaction between TMS site and TMS frequency in a two-way repeated-measures ANOVA such that the improvement in performance in the cognitive control task was site and frequency-specific. The effect size from the partial-eta square was 0.23, and the effect from a dependent t-test was 0.532, with 20 participants. The experimental design of this previous study is similar to the current study in that there are two sites for stimulation (lateral frontal and medial frontal) with two different stimulation frequencies (delta-beta and theta-gamma). Both studies used an arrhythmic condition to control for non-specific effects of TMS.

Sample Size Determination and Power Calculation: Based on this previous effect size, we estimated that our participant count at 24 participants is powered at >95%.

[figure not shown]

Figure 3. Power calculation for the interaction effect in two-way repeated-measures ANOVA modeled as within factors interaction in a two-way ANOVA with partial-eta square of 0.23, and a correlation between variables of 0.77 based on Riddle, Scimeca et al. 2021. Power calculation run using the G*Power software. Proposed number of participants is 24 and is depicted in red.

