Data will be collected until we reach 24 participants. Given the similarity with our previous experiment (Riddle, Scimeca, et al., 2020), we are confident that our current analysis will be sufficiently powered.

Secondary outcome: Rhythmic TMS to lateral frontal cortex at delta-beta frequency will increase frontal delta-beta coupling strength.

Previous Data: The planning and refinement of the proposed study was informed by our previous experiments. In our previous experiment, we delivered rhythmic TMS to lateral frontal cortex and found an increase in oscillatory power and an increase in phase entrainment specific to the targeted frequency band (Riddle, McPherson, et al.). In our previous experiment that delivered theta frequency TMS (4-8Hz) to lateral frontal cortex, we found an increase in oscillatory power in theta frequency (effect size of 0.540) and a robust increase in phase alignment across trials (effect size of 1.01). We use the phase alignment metric (inter-trial phase coherence) to estimate the required power to find a similar impact of delta-beta stimulation to align the phase of delta oscillations to task-modulated beta amplitude. The analysis of our previous experiment used 47 participants. Based on our previous effect size for entrainment, we would need 15 participants to reach 95% statistical power for this comparison. A more conservative estimate of a large effect size (0.60), we would need 24 participants to reach 80% statistical power.

[figure not shown]

Figure 4. Power calculation for increased phase alignment of delta oscillations to beta power from delta-beta TMS. The effect size estimate is based on phase entrainment in EEG from rhythmic TMS (larger effect, above). A more conservative effect size estimate would be to use the impact of rhythmic TMS on oscillatory amplitude (large effect, below). Both effect sizes were modeled as a dependent t-test using the G*Power software. The proposed number of participants is 24 and is depicted in red.

Data will be collected until we reach 24 participants. Given the similarity in methodology between the current experiment and our previous experiment (Riddle, McPherson, et al.), we are confident that we are sufficiently powered with 24 participants.

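### The secondary outcome's conservative power case uses an effect of 0.60, but its caption points to the oscillatory-amplitude effect, and the only such effect reported is 0.540 (about 72% power at n=24, against the 80% stated)

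*Combined protocol and SAP*

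**What the plan says.** Section 9.2, under the secondary outcome, reports two effects from an earlier theta-frequency TMS experiment. One is on oscillatory power: "we found an increase in oscillatory power in theta frequency (effect size of 0.540"). The other is on phase alignment across trials, 1.01. On the size of that experiment it says: "The analysis of our previous experiment used 47 participants".

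The phase-alignment effect is the declared planning basis: "We use the phase alignment metric (inter-trial phase coherence) to estimate the required power". It leads to 15 participants for 95% power. A second case follows: "A more conservative estimate of a large effect size (0.60), we would need 24 participants to reach 80% statistical power". No source is attached to 0.60.

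The Figure 4 caption describes the second case differently: "A more conservative effect size estimate would be to use the impact of rhythmic TMS on oscillatory amplitude". It adds that "Both effect sizes were modeled as a dependent t-test using the G*Power software". The section concludes that "we are confident that we are sufficiently powered with 24 participants".

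The planned analysis in Section 9.4.3 is a two-way repeated-measures ANOVA on values with the arrhythmic condition subtracted. Its hypothesis is an interaction between stimulation site and stimulation type. Section 9.2 gives an interaction-based calculation for the primary outcome (Figure 3) but none for coupling.

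**The concern.** A conservative case is there to show that the sample size still serves if the preferred effect is too optimistic, so its input should be traceable. Here it is not. The text labels 0.60 a large effect, and the caption gives the same label to the amplitude case, so the two appear to be one case. A reader who then looks for the amplitude effect finds 0.540, not 0.60.

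The gap matters because 0.60 lies almost exactly at the value where 24 participants reach 80% power, so a modest reduction takes the case below the level it is meant to show.

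A second, separate question is which contrast the effects describe. Both cases treat the effect as a single paired difference. The planned test is of a difference between two such differences, and its standardized effect need not be the same.

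**Working it through.** **Inputs.** Significance level 0.05 (Section 9.4.1). n = 24, effects 1.01, 0.60 and 0.540, and a dependent t-test (Section 9.2 and the Figure 4 caption). Section 9.2 does not state sidedness. Two-sided is taken from the non-directional alternative in Section 9.1 and is checked in step 1.

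**Formula.** For a paired t-test with standardized effect dz, df = n − 1 and noncentrality = dz × √n. Power is the probability that a noncentral t variable with these parameters falls beyond ±t(0.975, df).

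**Step 1: reproduce the plan's figures.**
- dz = 1.01, n = 15: noncentrality 1.01 × √15 = 3.91, power 95.3% (n = 14 gives 93.7%). The plan states 15 for 95%.
- dz = 0.60, n = 24: noncentrality 0.60 × √24 = 2.94, power 80.4% (n = 23 gives 78.5%). The plan states 24 for 80%.

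Both match. One-sided testing would need only 13 and 19 participants, so the two-sided reading is the one the plan used.

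**Step 2: the reported effect, same test.**
- dz = 0.540, n = 24: noncentrality 0.540 × √24 = 2.65, power 71.7%.
- For 80% power: n = 28 gives 78.7% and n = 29 gives 80.2%, so 29 are needed.
- Smallest effect with 80% power at n = 24: dz = 0.597.
- Declared planning effect, dz = 1.01, n = 24: power 99.7%.

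**Step 3: the contrast that is tested.** The interaction in Section 9.4.3 is (delta-beta − arrhythmic at dlPFC) − (theta-gamma − arrhythmic at dlPFC) − [the same at mPFC]. The arrhythmic terms cancel. What remains is D1 − D2, where D1 is delta-beta minus theta-gamma at dlPFC and D2 is the same difference at mPFC.

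For illustration, assume that only delta-beta at dlPFC shifts, that D1 and D2 have equal SDs, that the quoted effect d applies in full to D1, and that D1 and D2 have correlation r. Then

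dz(interaction) = d / √(2(1 − r)).

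Power at n = 24, two-sided 0.05:

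| d | r = −0.25 | r = 0 | r = 0.5 | r = 0.75 |
|---|---|---|---|---|
| 0.540 | dz 0.342, 36% | dz 0.382, 43% | dz 0.540, 72% | dz 0.764, 95% |
| 1.01 | dz 0.639, 85% | dz 0.714, 92% | dz 1.010, 99.7% | dz 1.428, over 99.9% |

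The interaction effect is smaller than the single-contrast effect when r is below 0.5 and larger when r is above 0.5. The documents give no r for coupling. Figure 3 quotes "partial-eta square of 0.23, and a correlation between variables of 0.77", but that correlation is between repeated measures of the primary outcome. It is not the correlation between two difference scores: if all the repeated measures are equally correlated, at 0.77 or any other value, r is 0.

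**The case against.** The strongest reply is that the printed statement is true. An effect of 0.60 does need 24 participants for 80% power, the text calls it only a large effect, and it never says that 0.60 was observed. The link to 0.540 runs through one conditional caption sentence. The text says power where the caption says amplitude, and these are not identical measures. Figure 4 is not shown. All of this stands. It means that 72% is the power at the only matching effect reported, not a demonstrated correction of 80%. It does not supply the missing source or make text and caption agree.

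It can also be said that 0.60 is compatible with the earlier data. If 0.540 is a paired effect from the 47 participants (an assumption), its 95% interval is about 0.23 to 0.84, which includes 0.60. But a value inside that interval and above the estimate is not conservative relative to the estimate.

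On the interaction, a reader might infer that the paired t-test is the wrong test. The documents do not support that. All four values per participant are within-person, so the one-degree-of-freedom interaction is itself a paired t-test on a double difference. What is open is whether the quoted effects describe that contrast, and the section does not say which contrast produced them.

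A reader might also take 43%, or 43% to 72%, as the power of the planned test. That rests on chosen values of r and on the other assumptions in step 3. Across the values of r shown, the result for 0.540 runs from 36% to 95%, so it is an illustration and not a finding.

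**Conclusion.** The point holds as a minor one. The stated 80% for the conservative case is not supported by the effect to which the caption attributes it. At the reported 0.540, the plan's own test gives 71.7% at n = 24, about 9 percentage points below the 80.4% for 0.60, and 80% would need 5 more participants (29 − 24). This assumes that the caption's amplitude effect is the one the text reports as oscillatory power. The power of the interaction on coupling is not stated and cannot be derived from the documents.

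A reader might infer that the trial is underpowered for its secondary outcome, or that 0.60 was picked to fit 24. Neither is supported. The declared planning effect of 1.01 gives 99.7% for the paired contrast and, under the step 3 assumptions, about 92% for the interaction at r = 0. The documents do not say why 0.60 was chosen. The consequence is further limited because 24 participants are justified separately for the primary outcome, the study is a pilot, and Section 9.4.1 treats a non-significant result as inconclusive.

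**What to change.** In Section 9.2, secondary outcome:

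1. State the power at the reported 0.540 as the conservative case: about 72% at 24 participants, with 29 needed for 80%. If 0.60 is kept, give its source and relabel it, for example as roughly the smallest effect detectable with 80% power at n = 24.
2. Make the text and the Figure 4 caption name the same measure and the same value.
3. Say that both cases describe a single paired contrast, and add the power of the site-by-type interaction on coupling under the authors' own stated assumptions, including the correlation between the two sites' difference scores. The values in the step 3 table should not be copied in as protocol text, and 0.77 from Figure 3 should not be used for that correlation.

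The cost is a few sentences, one caption check and one added calculation. The fallback power may read less favourably. No participants are added, and n = 24 and the planned ANOVA are unchanged.

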9.3 POPULATIONS FOR ANALYSES

Every effort will be made to ensure all enrolled and randomized participants complete all study sessions as described in this protocol. For this study, enrolled eligible healthy participants will be randomized to receive stimulation to frontal and parietal cortex in a randomized sequence. If a participant completes session 4, then they will be included in all analyses moving forward.

As previously stated in **Section 7 Study Intervention Discontinuation and Participant Discontinuation/Withdrawal**, enrolled participants who do not get randomized will be replaced. If required, then we will create additional blocks of 10 randomized sequences. Therefore, we will collect data until 24 participants complete the study and are eligible for analysis.

9.4 STATISTICAL ANALYSES

9.4.1 GENERAL APPROACH

All testing described below assumes a significance threshold of $p = 0.05$. Analyses will be deemed to be statistically significant if the p -value is less than this threshold. An analysis that does not exceed this threshold will be considered inconclusive. Continuous data will be described using means, standard deviations, and confidence intervals, while categorical data will be described using counts/percentages.

There may be additional covariates included in the analysis. Data will be assessed for normality and, if deemed necessary, corrective procedures will be applied (e.g., log normalization). Based on our previous dataset, we expect that the variables used here will be approximately Gaussian. However, if the distribution of a variable displays a skewed tail and a test for normality fails, then it is justified to use a corrective procedure. This correction will be applied upon consideration of the variables themselves, and not based on the result of the intended analysis.

Data will be collected until 24 participants complete the study and all data is usable. Given that recruitment will be feasible in a convenience sample, we expect to have complete data and all analyses will include the full participant pool. However, if there are technical errors that are not caught in time, then the affected analyses may have less participants. In this scenario, the data for a participant is then completely removed from the analysis.

The effects of stimulation are expected to be transitory, lasting for only a second or two after stimulation. For this reason, stimulation is delivered “online” immediately preceding the time at which the cognitive processes of interest are engaged. During each session, we include a control condition (arrhythmic TMS) that will be subtracted from the conditions of interest (delta-beta TMS and theta-gamma TMS). Therefore, we control for any effects of sequence or time within each session by subtracting each metric of interest from the condition-matched arrhythmic TMS metric. Furthermore, any learning effects from performing the reward-based decision-making task should be stabilized by the 3rd session. These methods are typical

in cognitive neuroscience paradigms. For the reasons listed above, it is unlikely that there will be any effect of sequence or carryover effects between sessions.

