stimulator output until a motor evoked potential (MEP) is generated: defined as a near-instantaneous increase muscle activity greater than 200 microvolts. Next, the intensity of single pulse TMS will be lowered until a MEP is generated on five out of ten pulses. This is defined as the motor threshold for the participant (Rossi et al. 2009). If the motor threshold cannot be determined via MEP, the experimenter will use visible twitches instead of MEP. Participants will receive 15 pulses of patterned TMS at 80% of their motor threshold during every trial. Patterned TMS takes three different forms (Figure 2). Delta-beta TMS delivers bursts of three pulses at 20 Hz (50 millisecond inter-pulse interval) with an inter-burst interval of 3 Hz (167 milliseconds). Theta-gamma TMS delivers bursts of three pulses at 50 Hz (20 millisecond inter-pulse interval) with an inter-burst interval of 5 Hz (200 milliseconds). As a control for the frequency-specificity of patterned TMS, arrhythmic TMS is delivered with a randomized inter-pulse intervals that are generated for each trial. The duration of arrhythmic TMS is randomly selected from a uniform distribution between the duration of delta-beta and theta-gamma TMS. The minimum inter-pulse interval will be 20 milliseconds. Between every train will be at least 11 seconds. An inter-train-interval of 11 seconds or greater allows for any residual effects of stimulation to return to baseline. This intensity, inter-pulse-interval, and inter-train-interval is well within the safety guidelines set forth for repetitive TMS (Wassermann, 1998; Rossi et al., 2009) and has been used in similar paradigms as the one described here. For example, Hermiller et al. 2020 delivered two seconds of theta-gamma patterned TMS (30 pulses per trial) at 80% of motor threshold (Hermiller et al. 2020). In addition, many other studies have delivered trains of TMS at higher intensities, upwards of 120% of motor threshold, on every trial of a cognitive task (Thut et al. 2011; Hanslmayr et al. 2014; Albouy et al. 2017)(Riddle et al. 2019; Riddle et al. 2020c; Sauseng et al. 2009). During a TMS session, participants will complete six blocks of 30 trials each. The participant will receive stimulation in either delta-beta, theta-gamma, or arrhythmic in a blocked design (the same stimulation is delivered for every trial in a block). The sequence of blocks will be randomized and counterbalanced such that each participant received each condition of TMS for 60 trials total. The third and fourth session of the experiment will be both be TMS sessions, where TMS is delivered to either the dorsolateral prefrontal cortex (dlPFC) or to medial prefrontal cortex (mPFC). The order and TMS sites will be randomized and counterbalanced across participants. Thus, at completion of the full experiment, participants will have received 12 blocks of 30 trials each of stimulation (180 trials per TMS session). In addition, two abbreviated blocks of TMS to mPFC and dlPFC will be administered at the end of the first session to assess for tolerability of TMS.

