6.3 MEASURES TO MINIMIZE BIAS: CONTROL CONDITIONS, RANDOMIZATION, AND PREREGISTRATION

Control Conditions

As discussed in section 4.2, it is not possible for the researchers to be blinded to the form of stimulation that is being used. However, the outcomes of the study are a comparison between experimental conditions with subtle temporal and spatial differences on the order of centimeters and milliseconds respectively. In brief, we will compare stimulation to dorsolateral prefrontal cortex to medial prefrontal cortex. The proximity of these regions is only a few centimeters and the associations of these regions to aspects of the task is under active investigation. In addition, we are comparing delta-beta patterned stimulation to theta-gamma patterned stimulation to an arrhythmic stimulation condition. The difference between delta-beta and theta-gamma stimulation is only a small difference in frequency, on the order of 100s of milliseconds. Similar to the stimulation site, the association of these frequencies of stimulation to task parameters is under active investigation and there are no online resources to draw these associations. Finally, we will use this task to calculate two distinct behavioral metrics: goal-directed behavior and reward-evaluation. These behavioral metrics are calculated from the same decision-making data and reflect different patterns of performance. In our previous study, we found that these two behavioral metrics were dissociable from each other (low correlation between these metrics across individuals). Thus, the paired association under investigation of delta-beta patterned TMS to goal-directed behavior during stimulation of dlPFC is fundamentally complex and none of these comparisons will be explained to the participant. Two of these three control conditions are included within each session and the site of stimulation is controlled between the third and fourth session. Thus, any systematic differences between sessions will be controlled by a within-session contrast of conditions. Finally, we prevent against unconscious experimenter bias in many ways that are described in section 4.2. To reiterate, conditions of

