9.4.2 ANALYSIS OF THE PRIMARY OUTCOME (BEHAVIOR)

Goal-directed behavior will be calculated as the average decision to perform the HARD task. The average of the two blocks for each stimulation conditions will be calculated (three stimulation types by two stimulation sites). A two-way repeated-measures analysis of variance (ANOVA) will be performed using within-participant factor of stimulation type (delta-beta TMS versus theta-gamma TMS; each subtracted by session-matched arrhythmic TMS) and within-participant factor stimulation site (dIPFC TMS versus mPFC TMS). We control for the effect of time with a subtraction of delta-beta TMS versus arrhythmic TMS and theta-gamma TMS versus arrhythmic TMS. In other words, four values are submitted to the ANOVA for each participant.

1. Delta-beta TMS to dIPFC minus arrhythmic TMS to dIPFC
2. Theta-gamma TMS to dIPFC minus arrhythmic TMS to dIPFC
3. Delta-beta TMS to mPFC minus arrhythmic TMS to mPFC
4. Theta-gamma TMS to mPFC minus arrhythmic TMS to mPFC

Thus, only differences from our active control, arrhythmic TMS, are considered meaningfully worth interpretation. We hypothesize to find an interaction between stimulation site and stimulation type in the ANOVA. Post-hoc differences will be investigated using Tukey's method to address multiple comparisons. We hypothesize that the predicted interaction will be driven by an increase in goal-directed behavior for delta-beta TMS to dIPFC. Sensitivity analyses will be conducted to evaluate the specificity of these effects: a similar analysis with reward-evaluation as the dependent variable and we do not expect that delta-beta TMS will have any effect on reward-evaluation.

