9.4.3 ANALYSIS OF THE SECONDARY OUTCOME (ELECTROPHYSIOLOGY)

Delta-beta phase amplitude coupling will be calculated between the phase of delta oscillations (2-3 Hz) in prefrontal electrodes (FCz and surrounding electrodes) and the amplitude of beta oscillations (15- 25 Hz) in left motor electrodes (C3 and surrounding electrodes). The instantaneous phase and amplitude of these oscillations will be calculated by averaging the signal in these two regions of interest, band-filtering the signal to the specified range, and then performing the Hilbert transform on the signal. Phase-amplitude coupling (PAC) is then calculated by creating a hybrid signal using the amplitude of beta oscillations in left motor electrodes and the phase of delta oscillations in prefrontal electrodes:

$$PAC = \left| \frac{\sum_{t=1}^N M * e^{i\theta}}{N} \right|, M \text{ is magnitude of beta oscillations, } \theta \text{ is angle of delta oscillations, } N \text{ is number of time points}$$

The PAC value is normalized by creating a null distribution by randomly shifting the beta timeseries by at least 10% of the number of time points. Then, PAC is calculated between the delta-phase timeseries and each of these randomly shifted beta-amplitude timeseries. Finally, PAC_z is calculated as the z-transformed true PAC value relative to the null distribution.

The average during the decision epoch of each trial of the task during stimulation will be calculated. The average of the two blocks for each stimulation conditions will be calculated (three stimulation types by two stimulation sites). A two-way repeated-measures analysis of variance (ANOVA) will be performed using within-participant factor of stimulation type (delta-beta TMS versus theta-gamma TMS; each subtracted by session-matched arrhythmic TMS) and within-participant factor stimulation site (dIPFC TMS versus mPFC TMS). We control for the effect of time with a subtraction of delta-beta TMS versus arrhythmic TMS and theta-gamma TMS versus arrhythmic TMS. In other words, four values are submitted to the ANOVA for each participant.

1. Delta-beta TMS to dIPFC minus arrhythmic TMS to dIPFC
2. Theta-gamma TMS to dIPFC minus arrhythmic TMS to dIPFC
3. Delta-beta TMS to mPFC minus arrhythmic TMS to mPFC
4. Theta-gamma TMS to mPFC minus arrhythmic TMS to mPFC

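### Balance low and high incentives 15/15 within each block, and correct the statement that subtracting arrhythmic TMS controls within-session time: a small precision gain, with no bias at issue

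*Combined protocol and SAP*

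**What the plan says.** **Incentives.** Section 6.3 (Randomization) randomises the offers and equalises the number of low ($2.50 to $4.00) and high ($4.50 to $6.00) values over a session. It mentions no balance within a block or condition. A session has six blocks of 30 trials, so 60 trials per condition. Section 8.1.2 gives an average reward-evaluation slope of 15% per $1 from the previous experiment.

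**Time within a session.** Section 9.4.1 says "we control for any effects of sequence or time within each session by subtracting each metric of interest from the condition-matched arrhythmic TMS metric". Section 9.4.2 says "We control for the effect of time with a subtraction of delta-beta TMS versus arrhythmic TMS", and 9.4.3 says "We control for the effect of time with a subtraction of delta-beta TMS versus arrhythmic TMS and theta-gamma TMS versus arrhythmic TMS". The matching is described in two ways: 9.4.1 has the wording just quoted, while 9.4.2 has "each subtracted by session-matched arrhythmic TMS". The predicted result in both analyses is a site-by-type interaction on four arrhythmic-subtracted values.

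**Related text.** Section 6.3 (Control Conditions) makes a narrower claim: "any systematic differences between sessions will be controlled by a within-session contrast of conditions". Section 4.3 says "The sequence of blocks will be randomized and counterbalanced". Section 6.3 adds that each condition appears in each half of the session and never twice running. Section 9.4.1 also says "There may be additional covariates included in the analysis" and names none.

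**The concern.** The primary outcome is the percentage of HARD choices, and the offered incentive drives it strongly. If offers are balanced only over 180 trials, two 60-trial conditions can differ in their incentive mix by chance. That difference enters the primary contrast as avoidable noise, and the study has only 24 participants.

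Separately, section 9.4 credits the arrhythmic subtraction with a property it lacks. A reader relying on 9.4 alone would think that time is handled by a step that drops out of the primary test, and would not see there the feature that does the work.

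**Working it through.** **1. The plan's power figure and the baseline used here.** Section 9.2 gives partial eta-squared 0.23, correlation 0.77, 24 participants and power above 95%. With f² = 0.23/0.77 = 0.299 and λ = N·m·f²/(1 − ρ), taking m = 2:
- ρ = 0.77: λ = 24 × 2 × 0.299/0.23 = 62.3, power above 0.999.
- ρ = 0: λ = 14.3, power 0.952.

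So the stated figure reproduces. The same section gives d = 0.532 from a dependent t-test with 20 participants. That is the same effect: √(0.299 × 19/20) = 0.533. Tested directly as a one-degree-of-freedom contrast (noncentral t, 23 df, two-sided 0.05), it gives 70.4% at n = 24. This is the baseline for measuring the gain below. Why it is lower than 95% is a separate question.

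**2. Incentive noise, balance per session only.** The eight levels have SD $1.146. At 15 points per $1:
- difference between two conditions: 15 × 1.146 × √(180/179) × √(2/60) = 3.15 points;
- interaction (two such differences): 3.15 × √2 = 4.45 points, variance 19.8.

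**3. Incentive noise, 15/15 split in each block.** Only variation within the low and high bands remains, with SD $0.559:
- difference: 15 × 0.559 × √(90/89) × √(2/60) = 1.54 points;
- interaction: 1.54 × √2 = 2.18 points, variance 4.74.

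As a check, counting low/high imbalance alone gives 3.88 points in the interaction, and √(3.88² + 2.18²) = 4.45. Exact balance over eight levels is impossible in 30 trials (30/8 = 3.75), so 15/15 is the practical target.

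**4. Effect on power.** Assume HARD choice near 50% (trial variance 2,500) and a participant-by-cell SD τ, which the documents do not give. The contrast variance is V = 4 × 2500/60 + 4τ². The effect is fixed at 0.532√V, and the split reduces V by 19.8 − 4.74 = 15.1.

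| τ (points) | V | Effect (points) | As planned | 15/15 split | Split plus incentive covariate |
|---|---|---|---|---|---|
| 0 | 166.7 | 6.87 | 70.4% | 74.4% | 75.8% |
| 5 | 266.7 | 8.69 | 70.4% | 72.9% | 73.7% |
| 10 | 566.7 | 12.66 | 70.4% | 71.6% | 71.9% |

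A simulation of binary trials at τ = 5 (4,000 runs in each of 24 settings) agrees. Raw-mean power was 69.8 to 71.5% with session-only balance and 72.7 to 74.8% with the split. Type I error of the raw-mean test was 4.6 to 5.5%, and mean estimates lay within 0.12 points of the truth.

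**5. What the subtraction does.** Write DB, TG and AR for the delta-beta, theta-gamma and arrhythmic means. At each site (DB − AR) − (TG − AR) = DB − TG, so AR cancels exactly from the interaction. AR stays in the separate difference scores and the site main effect, where it removes a level shared by the whole session.

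It does not remove a trend. Section 6.3 permits 6 × 4 = 24 orders. For any given pair of conditions, mean block position is equal in only 4 of them. The gap has mean 0, variance 1.375 and range −2 to +2 blocks. The zero mean is why a time trend common to the conditions causes no bias in the interaction, and it comes from the block order, not the subtraction.

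**The case against.** **Section 6.3 already names the right safeguard.** It states that the block scheme spreads each stimulation type over different phases of the session. Protocol and SAP are one document, so the text in 9.4 is a misattributed rationale, and correcting it changes no result. This stands.

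**The incentive point rests on silence.** The task code may already balance blocks, in which case the split gains nothing. Chance imbalance is also ordinary noise, already contained in the planning effect size as used here. The first part stands and limits the claim. The second does not make the noise worth keeping when it is nearly free to remove.

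**The gain depends on assumptions.** The 4-point gain requires every participant to respond alike (τ = 0); at τ = 10 it is 1.2 points. This stands too.

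A reader might also infer more than the documents support:
- *That the primary test is biased by time.* It is not, because the order is randomised with mean position gap zero.
- *That block position must be a covariate.* The documents give no drift, and 9.4.1 expects that "any learning effects from performing the reward-based decision-making task should be stabilized by the 3rd session". An assumed drift of 1 point per block costs only 0.7, 0.4 or 0.2 points of power at τ = 0, 5 or 10. It takes 3 points per block to cost 6.0, 3.8 or 1.8.
- *That an incentive-adjusted analysis should become primary.* Beyond the split it adds 1.3, 0.8 or 0.4 points. That is a weak reason to change the primary analysis in a study whose researchers are unblinded. Placed in 9.4.1, the covariate would also reach the reward-evaluation outcome, where the incentive slope is itself the outcome, and the participant-level correlations, where a trial-level covariate does not apply.
- *That the open covariate sentence is a serious flaw.* It is mainly missing detail. Choosing the best p-value among models with 1, 3 or 5 irrelevant covariates gave a simulated type I error of about 0.055, 0.062 or 0.065.

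**Conclusion.** This is a cheap improvement, worth considering. If 6.3 is followed as written, chance incentive imbalance contributes an SD of about 4.4 points to each participant's interaction contrast, and a 15/15 split per block halves it to about 2.2. The power gain is about 4.0, 2.5 or 1.2 points for τ = 0, 5 or 10, given d = 0.532, n = 24, 15 points per $1, HARD choice near 50% and no drift. It is nil if blocks are already balanced.

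The statements about time control in 9.4.1 to 9.4.3 are wrong as rationale, but the planned interaction test is unbiased with respect to common time trends and incentives. That conclusion assumes negligible block-to-block carryover. Because a condition never follows itself, a theta-gamma block follows a delta-beta block with probability 5/12, so a site-specific carryover could shift the contrast. Section 9.4.1 expects effects to last only a second or two, and 4.3 separates trains by at least 11 seconds.

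**What to change.** 1. **Section 6.3.** For sessions not yet run, balance low and high incentives 15/15 within every 30-trial block. If the task code already does so, say so. The cost is a small code change, and a mix of balancing schemes if some sessions have been run.
2. **Sections 9.4.1 to 9.4.3.** Replace the time-control sentences with text to this effect: subtracting session-matched arrhythmic TMS removes session-wide level differences from the separate difference scores and cancels from the site-by-type interaction; time within a session is handled by the randomised, restricted block order in 6.3. Use session-matched throughout. The cost is wording only.
3. **Optional, primary outcome only (9.4.2).** Prespecify an incentive-adjusted version of the same interaction test as a sensitivity analysis, and keep the raw-mean ANOVA as primary. The cost is one regression step on data already recorded. A single pooled incentive slope is a simplification, since 9.4.4 expects theta-gamma TMS to mPFC to raise that slope.
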